4.2. Potential Hy's Law criteria met

Previous text (revised/deleted text in bold):

If the patient does meet PHL criteria the Investigator will:

- Determine whether PHL criteria were met at any study visit prior to starting study treatment (See section **below on** Actions required when potential Hy's Law criteria are met before and after starting study treatment)
- Notify the AstraZeneca representative who will then inform the central Study Team
- The Study Physician contacts the Investigator, to provide guidance, discuss and agree an approach for the study patients' follow up and the continuous review of data. Subsequent to this contact the Investigator will:
 - Monitor the patient until liver biochemistry parameters and appropriate clinical symptoms and signs return to normal or baseline levels, or as long as medically indicated
 - Investigate the etiology of the event and perform diagnostic investigations as discussed with the Study Physician
 - Complete the three Liver CRF Modules as information becomes available
 - If at any time (in consultation with the Study Physician) the PHL case meets serious criteria, report it as an SAE using standard reporting procedures

Revised text (revised/added text in bold):

If the patient does meet PHL criteria the Investigator will:

- Determine whether PHL criteria were met at any study visit prior to starting study treatment (See section 6. Actions required when potential Hy's Law criteria are met before and after starting study treatment)
- Notify the AstraZeneca representative who will then inform the central Study Team
- Within 1 day of PHL criteria being met, the Investigator will report the case as an SAE of Potential Hy's Law; serious criteria 'Important

	medical event' and causality assessment 'yes/related' according to protocol process for SAE reporting.
•	For patients that met PHL criteria prior to starting IMP, the Investigator is not required to submit a PHL SAE unless there is a significant change [#] in the patient's condition
•	The Study Physician contacts the Investigator, to provide guidance, discuss and agree an approach for the study patients' follow up (including any further laboratory testing) and the continuous review of data.
•	Subsequent to this contact the Investigator will:
	 Monitor the patient until liver biochemistry parameters and appropriate clinical symptoms and signs return to normal or baseline levels, or as long as medically indicated.

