3.1 Inclusion criteria

For inclusion in the study patients should fulfill the following criteria:

- 1. Must have a life expectancy of at least 12 weeks.
- 2. Age ≥18 years at the time of screening. For patients aged <20 years and enrolled in Japan, a written informed consent should be obtained from the patient and his or her legally acceptable representative
- 3. Capable of giving signed informed consent which includes compliance with the requirements and restrictions listed in the informed consent form (ICF) and in this protocol. Written informed consent and any locally required authorization (eg, Health Insurance Portability and Accountability Act in the US, European Union [EU] Data Privacy Directive in the EU) obtained from the patient/legal representative prior to performing any protocol-related procedures, including screening evaluations. For patients aged <20 years and enrolling in Japan, a written informed consent should be obtained from the patient and his or her legally acceptable representative.
- 4. Disease not amenable to curative surgery
- 5. Eastern Cooperative Oncology Group (ECOG) performance status as defined in the specific module.
- 6. Body weight >30 kg.

- 7. No prior exposure to anti-PD-1 or anti-PD-L1, including on another AstraZeneca study. Exposure to other investigational agents may be permitted after discussion with the Sponsor.
- 8. Adequate organ and marrow function as defined below:
 - Hemoglobin $\geq 9.0 \text{ g/dL}$
 - Absolute neutrophil count $\geq 1.0 \times 10^9$ /L
 - Platelet count $\geq 75 \times 10^9/L$
 - Serum bilirubin ≤1.5 × the upper limit of normal (ULN). This will not apply to
 patients with confirmed Gilbert's syndrome, who will be allowed in
 consultation with their physician.
 - ALT and AST $\leq 2.5 \times$ ULN; for patients with hepatic metastases, ALT and AST $\leq 5 \times$ ULN
 - Measured creatinine clearance (CL) >40 mL/min or Calculated creatinine clearance (CL) >40 mL/min as determined by Cockcroft-Gault (using actual body weight)

Males:

Creatinine $CL = Weight (kg) \times (140 - Age)$ (mL/min) 72 × serum creatinine (mg/dL)

Females:

Creatinine $CL = Weight (kg) \times (140 - Age) \times 0.85$ (mL/min) $72 \times serum creatinine (mg/dL)$

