2.2 Protocol Deviations

2.2.1 Important Protocol Deviations

According to ICH E3 guidelines version dated 1995 (ICH 1995),

"Protocol deviations consist of any change, divergence or departure from the study design or procedures defined in the protocol. Important protocol deviations (IPDs) are a subset of protocol deviations that may significantly affect the completeness, accuracy, and/or reliability of the study data or that may significantly affect a patient's rights, safety or well-being."

For the interim analysis, all major deviations were classified as important deviations. For the final analysis, 4 general categories will be considered IPDs and will be listed and summarised.

- Deviation 1: Patients who deviate from key entry criteria per the Clinical Study Protocol v5.0 (CSP).
 - Inclusion Criterion 7: No prior exposure to anti-PD-1 or anti-PD-L1, including on another AstraZeneca study. Exposure to other investigational agents may be permitted after discussion with the Sponsor.
 - Inclusion Criterion 8: Adequate organ and marrow function as defined below:
 - Hemoglobin ≥9.0 g/dL
 - Absolute neutrophil count $\geq 1.0 \times 109 / L$
 - Platelet count \geq 75 × 109/L

- Serum bilirubin ≤1.5 × the upper limit of normal (ULN). This will not apply to patients with confirmed Gilbert's syndrome, who will be allowed in consultation with their physician.
- ALT and AST ≤2.5 × ULN; for patients with hepatic metastases, ALT and AST≤5 × ULN
- Measured creatinine clearance (CL) >40 mL/min or Calculated creatinine clearance (CL) >40 mL/min as determined by Cockcroft-Gault (using actual body weight)
- Inclusion Criterion A1: Histologically or cytologically confirmed locally advanced or metastatic urothelial ornon-urothelial carcinoma of the urinary tract (including the urinary bladder, ureter, urethra and renal pelvis)
- Inclusion Criterion A2: Disease that has progressed during or after at least one previous platinum or non-platinum-based chemotherapy, either for PD less than 12 months after adjuvant or neoadjuvant chemotherapy, or metastatic disease
- Inclusion Criterion A3: ECOG performance status 0-2
- Exclusion Criterion 3: Concurrent enrollment in another clinical study, or another substudy of this protocol, unless it is an observational (non-interventional) clinical study or during the follow up period of an interventional study

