For the parameters with no CTCAE grading that are listed in the CSP, shift tables from baseline to worst value on-treatment will be provided (Haemoglobin, Erythrocytes, LDH, TSH, Urea nitrogen.

Urinalysis

Additional summaries will include a shift table for urinalysis (Hemoglobin, Leucocytes, Glucose, Ketones, Protein) comparing baseline value to maximum on-treatment value.

Liver Enzyme Elevations and Hy's law

The following summaries will include the number (%) of patients who have:

- Elevated ALT, AST, and Total bilirubin during the study
- ALT $\geq 3x \leq 5x$, $> 5x \leq 8x$, > 8x. > 10x and > 20x Upper Limit of Normal (ULN) during the study
- AST $\ge 3x \le 5x$, $\ge 5x \le 8x$, $\ge 8x$. $\ge 10x$ and $\ge 20x$ ULN during the study
- Total bilirubin $\ge 2x \le 3x$, $\ge 3x \le 5x$, $\ge 5x$ ULN during the study
- ALT or AST $\ge 3x \le 5x$, $\ge 5x \le 8x$, $\ge 8x$, $\ge 10x$ and $\ge 20x$ ULN during the study
- ALT or AST $\ge 3x$ ULN and Total bilirubin $\ge 2x$ ULN during the study

(Potential Hy's law): The onset date of ALT or AST elevation should be prior to or on the date of Total Bilirubin elevation

• Narratives will be provided in the CSR for patients who have ALT \geq 3x ULN plus Total bilirubin \geq 2x ULN or AST \geq 3x ULN plus Total bilirubin \geq 2x ULN at any visit.

Liver biochemistry test results over time for patients with elevated ALT or AST (ie \geq 3x ULN), and elevated Total bilirubin (ie \geq 2x ULN) (at any time) will be plotted. Individual

patient data where ALT or AST (ie \geq 3x ULN) plus Total bilirubin (ie \geq 2x ULN) are elevated at any time will be listed also.

Plots of ALT and AST vs. Total bilirubin will also be produced with reference lines at 3×ULN for ALT, AST, and 2×ULN for Total bilirubin. In each plot, Total bilirubin will be in the vertical axis.

Assessment of Thyrotoxicity

Thyroid function tests free T3 and free T4 are to be measured 90 days after last dose during the safety follow up visit, per institutional care guidance only. Data obtained up until the 90 days following discontinuation of immunotherapy agents or until the initiation of the first subsequent therapy following discontinuation of treatment (whichever occurs first) will be used for reporting.

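### The liver count tables and the potential Hy's law row do not separate entry elevations from new or worsening ones in patients with hepatic metastases or Gilbert's syndrome

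*SAP*

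**What the plan says.** SAP 4.2.1, under Liver Enzyme Elevations and Hy's law, plans number and percentage of patients for rows such as "Elevated ALT, AST, and Total bilirubin during the study". Further rows cover bands of ALT, AST and either enzyme from 3×ULN, bands of bilirubin from 2×ULN, and the combination of ALT or AST ≥3×ULN with bilirubin ≥2×ULN. The combined row carries one extra rule: "The onset date of ALT or AST elevation should be prior to or on the date of Total Bilirubin elevation". No row refers to baseline or to worsening. The block does not use the on-treatment definition in SAP 3.1.

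The time window is open at the start. SAP 3.1.2.3 has laboratory data running from screening. The Laboratory assessments part of SAP 4.2.1 sets only an end: 90 days after immunotherapy stops, or the first subsequent therapy if sooner.

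The entry limits are in Protocol 3.1, criterion 8, and are repeated in SAP 2.2.1. The general enzyme limit is "ALT and AST ≤2.5 × ULN", with a wider limit "for patients with hepatic metastases, ALT and AST≤5 × ULN". Bilirubin may be up to 1.5×ULN, with an exemption for Gilbert's syndrome that begins "This will not apply to patients with confirmed Gilbert".

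**The concern.** The table thresholds overlap the entry limits in two groups. The hepatic-metastasis limit spans the whole ≥3× to ≤5×ULN enzyme band, and confirmed Gilbert's syndrome has no bilirubin ceiling. A patient in either group can be counted without any change on treatment. In the combined row, one of the two components can pre-date the first dose.

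This sits badly with two principles in the SAP itself. SAP 3.1.1 keeps adverse events that began before dosing out of most summaries unless they worsen. The Laboratory assessments text cuts data at subsequent therapy so that the summaries reflect study treatment alone. The liver rows guard against contamination after treatment but not before it. Hepatitis is a listed AESI, and SAP 4.1 says descriptive safety data may support health-authority considerations, so a reader should be able to interpret these counts as printed.

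**Working it through.** The plan states no figure for these rows, so there is none to reproduce. The check is to compare limits with thresholds and then apply the counting rules to constructed patients.

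**Thresholds against entry limits (×ULN)**

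| Group | Entry limit | Table threshold | Overlap |
|---|---|---|---|
| No hepatic metastases, ALT/AST | 2.5 | 3 | none |
| Hepatic metastases, ALT/AST | 5 | 3 | 3 to 5 |
| No Gilbert's, bilirubin | 1.5 | 2 | none |
| Confirmed Gilbert's, bilirubin | none | 2 | 2 and above |

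The problem is confined to the second and fourth groups. Enzyme bands above 5×ULN cannot be filled by unchanged values in eligible patients.

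**Constructed patients, sampled on days −5, 29, 57 and 85**

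| Patient | ALT row | Bilirubin row | Combined row |
|---|---|---|---|
| A. Neither condition; ALT 2.5, bilirubin 1.5, stable | no | no | no |
| B. Hepatic metastases; ALT 4 stable, bilirubin 1 | yes | no | no |
| C. As B, but bilirubin 2.5 from day 57 | yes | yes | yes |
| D. Gilbert's; bilirubin 2.5 stable, ALT 1 | no | yes | no |
| E. As D, but ALT 4 from day 57 | yes | yes | no if bilirubin is dated at first onset; yes if a later bilirubin date may be used |
| F. Both conditions; ALT 4 and bilirubin 2.5, stable | yes | yes | yes |
| G. New; ALT 1, then 4 from day 29; bilirubin 1, then 2.5 from day 57 | yes | yes | yes |

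B and D enter single-analyte rows with no change from entry. C enters the combined row with only bilirubin new. F enters it with nothing new. G is the only patient in whom both components arose on treatment, yet C, F and G are indistinguishable in the count. Dropping pre-dose samples changes none of these results, because B to F remain above threshold after dosing. A split by baseline status is needed as well as a window.

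**Size.** Patients counted in the ALT/AST rows from baseline alone = N × (share with hepatic metastases) × (share of those at ALT/AST ≥3×ULN at baseline). N is the planned 600 to 1200 for Module A (SAP 1.3). Both shares are assumptions: 10–40% and 1–10%.

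- N = 1200: 1200 × 0.10 × 0.01 = 1.2, to 1200 × 0.40 × 0.10 = 48.
- N = 600: 600 × 0.10 × 0.01 = 0.6, to 600 × 0.40 × 0.10 = 24.

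As a share of all patients this is 0.1% to 4.0%. The combined row would also need the rate of later bilirubin rise in these patients. The documents do not give it, so no estimate is offered.

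**The case against.** The strongest reply is that baseline is shown elsewhere. SAP 4.2.1 plans change from baseline for continuous laboratory values, and CTCAE shift tables that include ALT, AST and total bilirubin. Combined cases are also plotted over time, listed and narrated. Potential Hy's law is a screen, with other causes judged case by case. The primary outcome uses preferred-term groupings with treatment-emergent rules, and nothing here is tested. All of this is right and it limits the point. It does not remove it: shift tables take one analyte at a time and cannot say whether a combined case was new, while listings and narratives answer only patient by patient.

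Four stronger readings are tempting and are not supported.

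- That any patient may enter at 5×ULN. The limit applies only with hepatic metastases.
- That Gilbert's syndrome followed by an ALT rise completes a potential Hy's law case. With first-onset dating the ordering rule excludes it (patient E). It would appear in the narratives, which carry no ordering rule.
- That the SAP contradicts the protocol's liver appendix. The version history gives revised wording under which the investigator "is not required to submit a PHL SAE unless there is a significant change", but only for patients who met the potential Hy's law criteria before treatment. Patient C did not, so counting C agrees with that wording. It concerns SAE submission rather than tabulation.
- That the artefact matches the planning signal of 12 patients (1200 × 1%). That figure is for an AESI with 1% incidence, a different endpoint, and the size here is assumed.

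**Conclusion.** The gap is real but minor. The liver rows have no baseline or worsening condition, so unchanged entry values are counted in the ≥3× to ≤5×ULN enzyme rows (hepatic metastases) and in the bilirubin rows (Gilbert's). In a patient with hepatic metastases, an enzyme elevation present at entry can supply half of a potential Hy's law case. The range of about 1 to 48 of 1200 patients rests wholly on the two assumed shares and applies to the ALT/AST rows only; the true effect may be small. A reader might infer that the trial's hepatic safety findings are unsound. The documents do not support that, because the information needed to interpret each case is already planned. What is missing is a count that can be read without going back to individual patients.

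**What to change.** In the liver block of SAP 4.2.1:

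- Restrict the counts to post-dose values within the laboratory cut-off already stated in that section. Do not substitute the on-treatment window of SAP 3.1, which runs to 90 days without stopping at subsequent therapy.
- State that onset means the first date at or above the threshold, and whether a baseline sample can supply that date.
- Present each ALT, AST and bilirubin row in three parts: below the threshold at baseline (new); at or above it at baseline and worsened to a higher band; at or above it at baseline without worsening.
- Split the potential Hy's law row into both components below threshold at baseline, and either at or above it. Divide the second group by whether the elevated component worsened on treatment, so that real deterioration is not pooled with stable disease.
- Keep every case in the total, listings, plots and narratives, so that the split removes no possible signal.

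The cost is SAP wording and a baseline flag in tables already planned. Baseline is defined in SAP 3.1.3 and no new data are needed. The drawback is more rows with small counts.

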4.2.2 Efficacy data

Overall survival

OS will be summarised using the Kaplan-Meier method with median OS and its associated 95% confidence interval reported as well as the proportion of patients alive at 1, 2, 3, 4 and 5 years.

Objective Response Rate and Disease Control Rate

Objective response rate (ORR) and Disease control rate (DCR) at 6 and 12 months will be calculated for the SAF as the percentage of patients (%) with objective response and

controlled disease, respectively. ORR and DCR will be reported with the associated 95% exact Clopper-Pearson confidence interval.

The denominator used for ORR and DCR rates will be the number of patients with an assessment in the time period. A summary of investigator assessment (responding, stable or progressing) will be provided for those patients with an alternative method of assessment (e.g. WHO).

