2.3 Exploratory objective

1. To assess overall response rate (ORR) and disease control rate (DCR) based on Investigator assessed response to treatment (RECIST 1.1).

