2. ANALYSIS SETS

2.1 Definition of analysis sets

While some listings and tables may be produced based on all subjects screened, the following analysis population will be used for all analyses:

Safety Analysis Set (SAF): all enrolled patients who received at least 1 dose of durvalumab or tremelimumab.

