3.3.2 Exploratory endpoints

RECIST 1.1 response will be assessed by the investigator and not derived programmatically since tumor evaluation will be carried out by the sites per institution standards and detailed tumor measurements are not databased.

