3.3.2.1 Objective response

Objective response (using Investigator assessments) is defined as at least 1 visit response of CR or PR. Data obtained up until progression, or the last evaluable assessment in the absence of progression, will be included in the assessment of objective response. Patients who go off treatment without progression, receive a subsequent therapy, and then respond will not be considered responders.

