4. ANALYSIS METHODS

4.1 General principles

No hypothesis testing is planned for this single arm study. Each module will be summarised separately.

The general principles as mentioned below will be followed throughout the study:

- Descriptive statistics will be used for all variables, as appropriate, and will be presented separately for each module. Descriptive safety and efficacy data from the STRONG study may be utilized as supporting evidence for health authority considerations.
- Continuous variables will be summarized by the number of observations, mean, standard
 deviation, median, minimum, and maximum. For log transformed data it is more
 appropriate to present geometric mean, coefficient of variation (CV), median, minimum
 and maximum. Categorical variables will be summarized by frequency counts and
 percentages for each category.
- Unless otherwise stated, percentages will be calculated out of the population total.
- Exact CIs for proportions will be calculated using the Clopper-Pearson method.
- For percentiles of survival times based on the Kaplan-Meier method (eg, median survival), CIs will be calculated using the default method available in the SAS LIFETEST procedure (ie, the Klein and Moeschberger extension of the Brookmeyer-Crowley method).
- For point-estimates of survival based on the Kaplan-Meier method (eg, for OS at 12 months), CIs will be calculated using the default method available in the SAS LIFETEST procedure (ie, using Greenwood's estimate of standard error and a log-log transformation).
- For continuous data the mean and median will be rounded to 1 additional decimal place compared to the original data. The standard deviation will be rounded to 2 additional decimal places compared to the original data. Minimum and maximum will be displayed with the same accuracy as the original data.
- For categorical data, percentages will be rounded to 1 decimal place.
- SAS® version 9.3 or higher will be used for all analyses.

Baseline will be the last assessment of the variable under consideration prior to the intake of the first dose of study treatment.

All data collected will be listed.

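### ORR and DCR are labelled as rates for all treated patients but divide only by assessed patients, so with the same numerator they can only equal or exceed the all-treated rates

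*SAP*

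**What the plan says.** SAP 4.2.2 states that ORR, and DCR at 6 and 12 months, "will be calculated for the SAF as the percentage of patients (%) with objective response" or with controlled disease. SAP 2.1 defines that set as "all enrolled patients who received at least 1 dose of durvalumab or tremelimumab"; no post-baseline assessment is required. The next paragraph of 4.2.2 fixes the divisor: "The denominator used for ORR and DCR rates will be the number of patients with an assessment in the time period". This departs from the default in SAP 4.1: "Unless otherwise stated, percentages will be calculated out of the population total".

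Both numerators require a recorded response. SAP 3.3.2.1: "Objective response (using Investigator assessments) is defined as at least 1 visit response of CR or PR". SAP 3.3.2.2 requires a best response of CR, PR or SD within the first 6 or 12 months.

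There is no common imaging schedule. SAP 3.3.2 explains that "tumor evaluation will be carried out by the sites per institution standards and detailed tumor measurements are not databased", and Table 2 of the protocol likewise leaves tumour assessment to institutional standard. Patients assessed by another method, such as WHO, get a separate summary under SAP 4.2.2. The objective in Protocol 2.3 is response by RECIST 1.1.

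**The concern.** A percentage presented for the safety analysis set will be read as a share of all treated patients. Under the SAP rule it is a share of the patients who were assessed. The patients left out may include those who die, deteriorate or stop treatment before any assessment is recorded, and for a response endpoint these are treatment failures. Nothing in the SAP counts them as failures or specifically asks for their number.

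The same divisor carries into the ORR and DCR subgroup summaries in SAP 4.2.1 (age, ECOG status, stage, PD-L1 and others). If the unassessed share differs between subgroups, part of any visible difference comes from the denominator.

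A second gap sits in the same paragraph. The SAP does not say whether patients assessed only by another method belong in the ORR/DCR denominator, so two programmers could produce different rates.

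The stakes are moderate. ORR and DCR are exploratory, and no hypothesis is tested. However, SAP 4.1 allows descriptive efficacy data to serve as supporting evidence for health authorities, and for that use the meaning of the percentage must be clear.

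**Working it through.** **Inputs.** The denominator rule and the analysis set come from SAP 4.2.2 and 2.1, the numerators from SAP 3.3.2.1 and 3.3.2.2, and the exact Clopper-Pearson interval from SAP 4.2.2. N = 800 is a row of SAP Table 1. The plan states no expected ORR or DCR and no expected unassessed share, so it has no figure of its own to reproduce on this point. Its one sample-size probability (SAP 1.3: over 75% chance of at least ten events at 1% incidence with 1200 patients) does reproduce, at 0.759, but it concerns AESIs.

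**Direction.** Let n be the treated patients, m ≤ n those with an assessment, and x the responders (or patients with disease control). Every one of the x is among the m, because a recorded response is an assessment. Hence

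x/m ≥ x/n,

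with equality only if m = n or x = 0. A check of every combination with n up to 120 found no exception. The comparison holds the numerator fixed: patients assessed only by another method are not RECIST 1.1 responders in either rate.

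**Size.** With u = 1 − m/n,

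reported rate = x / [n(1−u)] = all-treated rate × 1/(1−u).

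The multiplier is 1.020 at u = 2%, 1.053 at 5%, 1.111 at 10% and 1.250 at 20%. It does not depend on n.

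**ORR illustration.** 136 responders among 800 treated; the 17.0% and every value of u are assumptions.

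| u | Assessed | Reported ORR (95% CI) | Shift in points |
|---|---|---|---|
| 0% | 800 | 136/800 = 17.0% (14.5–19.8) | – |
| 2% | 784 | 136/784 = 17.3% (14.8–20.2) | +0.3 |
| 5% | 760 | 136/760 = 17.9% (15.2–20.8) | +0.9 |
| 10% | 720 | 136/720 = 18.9% (16.1–21.9) | +1.9 |
| 20% | 640 | 136/640 = 21.3% (18.1–24.6) | +4.3 |

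**DCR illustration.** The multiplier is the same, so a higher base rate moves by more points. With 480 controlled among 1200 treated (40.0%, 37.2–42.8, also assumed), the reported rate is 480/1080 = 44.4% (41.5–47.5) at u = 10% and 480/960 = 50.0% (46.8–53.2) at u = 20%.

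**Subgroup illustration.** Take the same assumed all-treated ORR of 17.0% in both ECOG groups.
- u = 5% in ECOG 0–1 and 10% in ECOG 2: 17.0/0.95 = 17.9% against 17.0/0.90 = 18.9%.
- u = 5% and 20%: 17.9% against 17.0/0.80 = 21.3%.

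In both cases the whole difference comes from the denominator.

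**The case against.** The strongest reply is that this is an openly stated choice. SAP 4.1 permits exceptions to the population-total default, and 4.2.2 makes one directly after naming the analysis set. An analysis set and an evaluable denominator can legitimately differ; SAP 3.1.2.3 does the same for laboratory grades. If the tables show the denominator, a reader can subtract to find the number unassessed. The endpoints are exploratory, and SAP 4.2.1 rules out formal subgroup comparisons.

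The size is also unknown. Investigator response is recorded at treatment visits and at the 90-day visit (Protocol 4.2.2 and 4.3), and some patients who discontinue have one further scan if clinically feasible (Protocol 1.4). The unassessed share may therefore be small. The documents do not settle it: Protocol 7.2.1 has some patients followed until confirmed progression after stopping, while Protocol 5.1 foresees no efficacy assessment beyond survival and the investigator's evaluation before each dose.

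Finally, with scan timing left to institutions, counting every unassessed patient as a failure can understate the true rate.

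Much of this stands, and it limits the weight of the point. It does not remove the upward shift. Disclosing a rule does not make an assessed-only percentage a rate for all treated patients, and the absence of formal comparisons does not correct the subgroup rates themselves. The risk of understatement is a reason to show both rates. It is not a reason to show only the higher one.

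**Conclusion.** The concern holds. Given the same numerator, the direction is certain: the SAP rule yields rates at or above the all-treated rates, overall and in each subgroup. The size depends on an unassessed share that the documents do not give. At an assumed 17.0% ORR, the shift is under one point if 5% or fewer are unassessed and about four points at 20%; for DCR the shift in points would be larger at a higher base rate.

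This should be changed because the change is cheap and the data may be shown to authorities. It does not threaten the primary AESI analysis or OS. The protocol refers to the tumour modules for statistical detail, and the Module A text was not available for this review, so the conclusion covers the SAP as written.

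**What to change.** In SAP 4.2.2:

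- Make all patients in the safety analysis set the denominator for the main ORR and DCR, overall and in every subgroup. Count patients with no response assessment as non-responders, or as not controlled.
- Report the number unassessed, overall and by subgroup.
- Keep the assessed-only rate as a labelled sensitivity analysis, and state its time period for ORR. SAP 3.3.2.1 sets no time limit, whereas DCR has 6 and 12 months.
- For patients assessed only by another method, report their number and keep their separate summary. State that they are not RECIST 1.1 responders in the main rate, and add a sensitivity rate that either excludes them or counts their investigator-assessed responses.

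**Cost.** SAP wording, one denominator change, two sets of counts and two labelled sensitivity rates, all from response data already collected. The main rates will be lower or unchanged. They will be conservative where an assessment is missing for reasons unrelated to outcome, or where a response was recorded only by another method. Showing the sensitivity rates alongside covers this.
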